#### **Screening & Pre-surgical procedures**

The medical history and vitals (heart rate and blood pressure) will be taken. In addition, clinical photographs and one standardized periapical radiograph will be completed. A CBCT scan will be taken before implant placement for screening eligibility, and impressions will be taken for surgical guide preparation. The CBCT scan may be scheduled separately due to availability of the CBCT machine.

#### Randomization and masking of examiners

The randomization of the patients to either the test (5-mm implant) or control group (10-mm implant) is determined using a computer-generated randomization list (www.random.org). After administration of a local like 2% Lidocaine with 1:100k epinephrine, sulcular incisions at the adjacent teeth and a midcrestal incision will be performed, allowing reflection of a full-thickness flap. At this stage, the randomization concealment will be broken, and the surgical site will be prepared according to the manufacturer's instructions.

#### Surgical procedures

The medical history and vitals (heart rate and blood pressure) will be taken prior to the surgical procedure. In addition, clinical photographs will be taken during the surgical procedure. An implant surgical guide for partially edentulous patients will be fabricated according to procedure previously described by Shotwell (Shotwell et al. 2005).

#### Experimental group (GS)

5.0 mmL x 5.0mmD Zimmer T3 Short Ex Hex With Discrete Crystalline Deposition (DCD) implants:

1. Crestal incision and flap elevation

- 2. ACT Short Pointed Started Drill will be used to penetrate the cortical bone to the first depth mark on the drill. The recommended drill speed is 1200-1500 rpm. Copious irrigation with sterile saline solution is planned to prevent overheating of the bone during high speed drilling.
- 3. 2.0 mm ACT Short Twist Drill will be to drill to the bottom of the depth mark for 5.0 mm length implants. The recommended drill speed is 1250 rpm.
- 4. The direction and position of the preparation is verified by inserting the narrow end of the direction indicator into the osteotomy. A suture will be threaded through the hole to prevent accidental swallowing.
- After proper alignment is verified using the Direction indicator, the 3.25 mm ACT Short Twist Drill will be used to drill until the bottom of the depth mark for 5 mm implants with a speed 1250 rpm.
- Once the coronal aspect of the osteotomy has been prepared the 3.85mm ACT Short Twist Drill will be used to Drill to the bottom of the depth mark for 5.0mm. The recommended drill speed is 1250 rpm.
- The 3.85 mm Short Shaping Drill with a yellow band indicating that it is for use with a 5.0mmD T3 Short Implants. The recommended drill speed is 1250 rpm.
- Tapping Step for dense bone (Type I) using the Handpiece Connector advancing the tap into the prepared site at approximately 15-20 rpm. Final seating of the Short Dense bone Tap may require the use of the Ratchet Extension and the Ratchet Wrench.
- 9. The implant will be placed into the prepared site at approximately 15-20 rpm. Final seating of the implant may require the use of a Ratchet Extension and Ratchet Wrench.
- 10. To remove the implant mount, Open End Wrench will be placed onto the mount. The screw is loosened at the top of the mount with a Large Hex Driver or Large Hex Driver Tip inserted into the Right-Angle Driver or Low Torque Indicating Ratchet Wrench and rotate counter-clockwise. After the screw is completely loosened, the Open End Wrench will be rotated counter-clockwise slightly before removing the mount. The mount can be carried from the mouth with the Open End Wrench.
- 11. Cover Screw from the No-Touch Implant Tray with the Small Hex Driver (PHD00N) is placed onto the implant at no more than 10 Ncm.
- 12. Soft-tissue flaps will be secured and repositioned with sutures.
- 13. Final periapical radiograph is taken.

### Control group (GL)

10 mmL X 5.0mmD Zimmer T3 with DCD Ex Hex Parallel Walled implants

- 1. A midcrestal incision is made, with full thickness flap reflection. Then sutures will be used to assist flap reflection both on the buccal and palatal sides.
- 2. Implant sites are marked with a 2.0mm round bur drill and prepared to a depth of 1.0 mm from the sinus floor with first 2 osteotome drills (up to 2.8 mm wide).
- 3. 2.8 mm reamer (SCA kit, Neobiotech, Seoul, South Korea) will then be inserted with different stoppers until the sinus membrane wall is fractured.
- 4. After the sinus membrane wall is fractured, a gauge will then be applied to check sinus wall surrounding to ensure membrane is lifted from the sinus wall.
- 5. Subsequently, bone graft (human allograft) small particle (size 250μm to 850 μm) will be inserted into the osteotome sites then slowly tapped into the sinus floor either by bone inserter/spreader (SCA kit, Neobiotech, Seoul, South Korea) or osteotome instrument by mallet. These instruments should not enter the sinus cavity.
- 6. The sinus floor should be elevated to at least 2 mm height longer than the desired implant length due to bone shrinkage occurring after healing.
- 7. Implant osteotome drills will be used to drill the osteotome site to the final diameter size according to the manufacturer's guideline, but only to the level of remaining bone height. Again, the instruments should not enter the sinus cavity to avoid any potential perforation.
- 10mm length of Zimmer T3 with DCD Ex Hex Parallel Walled implant will be placed into the prepared hole.
- 9. Cover Screw is placed onto the implant at no more than 10 Ncm.
- 10. Soft-tissue flaps will be secured and repositioned with sutures.
- 11. Final periapical radiograph is taken.

All surgeries will be performed under local anesthesia using one or more of the following medications:

- Lidocaine with epinephrine, (Xylocaine 2%®-Epinephrine 1:100,000 and 1:50,000, Dentsply Pharmaceutical, York, PA, USA).
- Articaine (Septanest 4%®-Epinephrine 1:100,000, Dentsply Pharmaceutical, York, PA, USA).
- Mepivacaine (Polocaine 2%®-Levonordefrin 1:20,000, Dentsply Pharmaceutical, York, PA, USA)."

#### **Post-surgical instructions**

All subjects will be prescribed and instructed to take the following oral antibiotics after surgery: 500 mg amoxicillin (GlaxoSmithkline) three times per day for 7 days, or 300 mg clindamycin (if allergic to penicillin) four times per day for 7 days. In addition, 600 mg of ibuprofen (Brufen; Abbott S.R.L., Latina, Italy) as needed, and chlorhexidine mouthwashes 0.12% twice daily for 2 weeks. Subjects with a removable prosthesis will be instructed to not wear them during the healing phase. The sutures will be removed after 2 weeks. Any surgical complication will be recorded such as infection, pain, and other adverse events.

#### **Prosthetic placement**

After 4 months of submerged healing, exposure of the implant and placement of a healing abutment is performed. After 2 weeks, the sutures are removed. After 5 months of submerged healing, impressions via pick-up impression copings are taken either using a polyether material (Impregum 3M/ESPE, Neuss, Germany) and/or a digital scan (TRIOS, 3Shape, Denmark). Within 1 to 3 weeks, definitive screw-retained metal-ceramic or metal-resin restorations are delivered.

#### Follow-up evaluation visits

Follow-up evaluation (2 weeks)

- Clinical photographs
- Suture removal
- > VAS on pain
- Patient satisfaction
- ➢ Implant mobility
- Plaque index

Follow-up evaluation (4 months) for stage 2 implant (Installment of abutment)

- Clinical photographs
- Standarized Periapical Radiograph
- ► ISQ
- ➢ Implant mobility
- > Plaque index

Follow-up evaluation (4 months and 2 weeks) for post-op and impression

- Post-op stage 2 implant, remove suture
- > Implant mobility
- Plaque index

Follow-up evaluation (5 months) for post-op and impression

- Impression definitive crown
- ➢ Implant mobility
- > Plaque index

Follow-up evaluation (5 months and 2 weeks) for crown placement and maintenance

- Implant maintenance
- Definitive Crown placement
- > Clinical photographs and standardized periapical radiographs.
- ➢ Implant mobility
- Plaque index

Follow-up evaluation (6 months after crown placement)

- Clinical measurements evaluation
- ➢ Implant maintenance
- > Clinical photographs and standardized periapical radiographs.
- Patient satisfaction
- Implant mobility
- Plaque index

Follow-up evaluation (12 months after crown placement)

- Implant maintenance
- ➢ Implant mobility
- Plaque index

Follow-up evaluation (18 months after crown placement)

- Clinical measurements evaluation
- > Clinical photographs and standardized periapical radiographs.
- Patient satisfaction
- Implant maintenance
- ➢ Implant mobility
- > Plaque index

## DATA MANAGEMENT

Data reflecting participant experience with the protocol under investigation will be reported to the Principal Investigator and the data recorded on Case Report Forms (CRF). CRF will be signed and

dated by the investigator or a designated representative and filled out in black ink. If an entry on a CRF requires change, the correction will be made as follows:

a. A single line will be drawn through the incorrect entry.

b. The date will be entered and the change initialed. White-out or erasure on CRFs will not be permitted under any circumstance.

All fields and blanks must be completed. The following abbreviations will be used when values or answers cannot be provided: NA=not applicable; ND=not done, UNK=not known. Completed original CRF's will be collected by the Principal Investigator. CRF must be submitted for each subject. Database entry will proceed directly from the CRF for analysis. The data, as well as group/subject identification, will be made available to the investigator at the conclusion of the study.

The study coordinator will audit all CRFs and corresponding portions of School of Dentistry records. The monitoring will provide the Principal Investigator the opportunity to evaluate the progress of the study and to verify the accuracy and completeness of the CRFs; assure that all protocol requirements, applicable FDA regulations and investigator's obligations are being fulfilled, and to resolve any inconsistencies in the study records. The Principal Investigator may stop the study if it is observed that the protocol or sound clinical practices are not being followed. The Principal Investigator may exclude subjects from the study if review of their records indicates violations of the protocol or if there were other reasons to believe that their inclusion would jeopardize the validity of the study.

All research records will be labeled "confidential" and kept in a locked room in a locked cabinet with limited access or in a password protected computer program. Only those directly involved with this research study will have access to the research records and password. A description of this clinical trial will be available on http://www.clinicaltrials.gov/, as required by U.S. Law. This Web site will not include information that can identify the patient.

The study coordinator and investigator will make an accurate and adequate written progress reports to the IRB at appropriate intervals not exceeding one year. The investigator will make an accurate and adequate final report to the IRB within 3 months after completion or termination of the study. The investigator will make an accurate and adequate special report to the IRB on any serious unexpected or life-threatening adverse event or death occurring in relationship to the study whether regarded as study-related or not.

On completion of the study, the investigators will prepare a final report of the study results.

#### STATISTICAL CONSIDERATIONS

The study will be powered to detect a minimum clinically significant difference in bone loss of 0.5 mm using  $\alpha = 0.05$ , a power  $(1 - \beta) = 80\%$ . Considering possible dropouts, the number of patients will also be increased by 10% for each arm. On the basis of this data, the minimum needed number of patients to be enrolled in this study is 17 with for the test group (GS) and 17 for the control group (GL). Mean values, standard deviations, and medians will be calculated for the clinical parameters. The association between crown-implant ratio and final bone loss as well as prosthetic complications will be examined. Changes of the parameters over time within the two groups as well as differences between groups will be analyzed using repeated measure of analysis of variance (ANOVA).

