#### Primary and secondary endpoints

Primary endpoint: Comparing mesial-distal (M-D) bone loss between the two groups (Radiologic outcome)

Secondary endpoints: Clinical outcomes and Patient reporting outcomes

- 1. Determine the survival rate and success rate of the Group Short (GS) and Group Long (GL) group.
- 2. Compare incidence and types of surgical and prosthetic complications between groups
- 3. Compare the number of sites with bleeding on probing (BOP)
- 4. Compare the cost of both procedures and the cost of the prosthetic complications
- 5. Compare the probing pocket depth (PPD)
- 6. Determine the pain after treatment: Visual analog score (VAS)
- 7. Compare patient satisfaction
- 8. Compare surgical time

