#### **STUDY PROCEDURES**

#### **Clinical measurements**

1) The following measurements will be taken for each treated implant by a blinded, calibrated examiner at the implant placement (surgery V2), at the time of prosthetic placement (5-month postop V6), 12-month follow-up (V8), and 24-month follow-up (V10).

- Marginal bone level (MBL): It will be calculated based on standardized radiographs using registered bite-block with a Rinn (Dentsply Rinn, Elgin, IL, USA) film holder and expressed as the distance from the implant shoulder to the most coronal bone-to-implant contact (BIC) on the mesial and distal side of the implant. The mean values will be calculated for each implant at the time of implant placement, at the time of prosthetic placement (5-month post-op V6), 12-month follow-up (V8), and at 24-month follow-up (V10). In the case that the bone levels around the study implants are hidden or difficult to read, new radiographs will be taken. Peri-implant marginal bone levels will be measured using the ImageJ software\* (ImageJ, U. S. National Institutes of Health, Bethesda, Maryland, USA) (Schneider et al., 2012). The software will be calibrated for every single image using the known implant length or the length of the implant collar. Measurements of the mesial and distal bone crest level adjacent to each implant will be rounded to the nearest 0.1 mm. Implants with bone up to the coronal margin of the implant collar will be given a value of zero. Mesial and distal measurements of each implant are averaged, and a mean calculated at patient level and then at group level.
- PPD and BOP: It will be assessed at 4 sites per implant (mesial, distal, buccal, and palatal) with a measurement stent using a periodontal probe (UNC, Hu-Friedy, Chicago, IL, USA). PPD are measured from the distance of the mucosal margin to the bottom of the probable pocket in mm. BOP is recorded using the following scoring method: 0) no bleeding 1) an isolated bleeding spot is visible, 2) blood forms a confluent red line on margin, and 3) heavy or profuse bleeding.
- Plaque: The level of oral hygiene will be evaluated using the Modified gingival index (Lobene et al., 1986) (Scores 1-4).

0 = Absence of inflammation

1 = Mild inflammation or with slight changes in color and texture but not in all portions of gingival marginal or papillary

2 = Mild inflammation, such as the preceding criteria, in all portions of gingival marginal or papillary

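### Repeated-measures ANOVA is planned for bone level with no sphericity handling and no primary contrast, so the 5% error rate for the bone-loss comparison is not assured

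*Combined protocol and SAP*

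**What the plan says.** Statistical Considerations names one inferential method: changes within groups over time and "differences between groups will be analyzed using repeated measure of analysis of variance (ANOVA"). It sets alpha at 0.05 and 80% power for a "minimum clinically significant difference in bone loss of 0.5 mm". It does not say whether the univariate, multivariate or mixed-model form is meant, which visits enter, which term or contrast is primary, or what is done about sphericity.

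Primary and Secondary Endpoints defines the primary endpoint as "Comparing mesial-distal (M-D) bone loss between the two groups (Radiologic outcome"), again with no time point.

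Clinical Measurements has marginal bone level (MBL) read at implant placement (V2) and "at the time of prosthetic placement (5-month postop V6), 12-month follow-up (V8), and 24-month follow-up (V10"). Two rules there affect the spread of values: "Implants with bone up to the coronal margin of the implant collar will be given a value of zero", and "Measurements of the mesial and distal bone crest level adjacent to each implant will be rounded to the nearest 0.1 mm". The zero rule is not restricted to placement. The unit of analysis is the patient: "Mesial and distal measurements of each implant are averaged, and a mean calculated at patient level and then at group level".

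No SD, variance by visit or between-visit correlation appears anywhere in the document.

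**The concern.** A univariate repeated-measures ANOVA judges every within-patient comparison, including group-by-time, against a single error averaged over all visits. That average is right for a particular difference only under sphericity, meaning that the difference between any two visits has the same variance.

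Bone level gives reason to doubt this. Spread may be small at placement, and the zero floor may contribute to that. The same implant is then filmed repeatedly with a registered bite-block, so follow-up readings may be highly correlated, and their spread may widen with time. Placement-to-last change would then be the most variable difference, tested against an error averaged with quieter ones. Its interval would be too narrow and false positives would exceed 5%. This comparison is the primary endpoint, and the plan names no other test.

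**Working it through.** **The plan's own figure.** The usual two-sample formula for a 0.5 mm difference, two-sided alpha 0.05 (sidedness is not stated) and 80% power is n = 2(1.960 + 0.842)²σ²/0.5² = 62.8σ² per arm. Dropout is covered by the statement that "the number of patients will also be increased by 10% for each arm". Fifteen evaluable patients give 15 × 1.1 = 16.5 or 15/0.9 = 16.7, both rounding up to the stated 17. Rounding up to 15 requires σ of about 0.47 to 0.49 mm. The 17 is therefore reachable, but it cannot be verified because no SD is stated.

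**Pooled error against own error.** For four visits, the expected within-patient error mean square is MS = (mean of the four variances) − (mean of the six covariances). The pooled method takes the variance of any between-visit difference to be 2MS. The true variance for bone loss is var(last) + var(placement) − 2cov.

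*Assumed setting A:* every placement value is zero, and the three follow-up visits have a common SD s and correlation ρ.

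- MS = 3s²/4 − 3ρs²/6 = s²(0.75 − 0.5ρ), so 2MS = s²(1.5 − ρ).
- The true variance of bone loss is s².
- Pooled SE / true SE = √(1.5 − ρ). The ratio does not depend on s.
- The ratio is exactly 1 at ρ = 0.5, where sphericity holds: the difference between two follow-up visits has variance 2s²(1 − ρ) = s². The pooled SE is too small above 0.5 and too large below it.

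*Assumed setting B, mild widening:* placement zero; follow-up SDs 0.40, 0.45 and 0.50 mm; ρ = 0.5. MS = 0.6125/4 − 0.3025/6 = 0.1027. Ratio = √(0.2054/0.25) = 0.91.

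*Assumed setting C, stronger widening:* placement zero; SDs 0.3, 0.4 and 0.5 mm; correlation 0.8 between adjacent visits and 0.64 two visits apart. MS = 0.50/4 − 0.352/6 = 0.0663. Ratio = √(0.1327/0.25) = 0.73.

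**Rejection rates when the arms do not differ.** Simulation with 17 per arm and 20,000 trials per setting:

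| Setting | SE ratio (formula) | Contrast, pooled error | Group-by-time F, uncorrected | Same F, Greenhouse-Geisser | Change, own error | Group main effect |
|---|---|---|---|---|---|---|
| A, ρ = 0.2 | 1.14 | 2.7% | 5.4% | 4.3% | 5.0% | 5.2% |
| A, ρ = 0.5 | 1.00 | 4.8% | 4.9% | 4.4% | 4.8% | 4.9% |
| A, ρ = 0.7 | 0.89 | 7.9% | 5.3% | 4.3% | 5.0% | 4.8% |
| A, ρ = 0.8 | 0.84 | 10.3% | 6.6% | 4.8% | 5.2% | 5.0% |
| A, ρ = 0.9 | 0.77 | 12.8% | 8.4% | 4.8% | 4.8% | 4.8% |
| B | 0.91 | 7.4% | 5.0% | 4.2% | 5.0% | 4.9% |
| C | 0.73 | 15.4% | 7.3% | 4.9% | 5.0% | 4.9% |

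With a partial floor (54% zeros at placement, values floored at zero and rounded to 0.1 mm at every visit), the pooled-error contrast runs from 3.7% at ρ = 0.2 to 10.1% at ρ = 0.9, and the group-by-time F from 4.8% to 5.7%. At 25 per arm, the enrolment ceiling of 50, the pattern is the same: 2.6% in A at ρ = 0.2 and 15.8% in C for the pooled-error contrast.

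**What the group main effect estimates.** It averages the between-arm difference in level over all four visits. If the arms are equal at placement and differ by 0.5 mm at each later visit, it estimates (0 + 0.5 + 0.5 + 0.5)/4 = 0.375 mm. If they differ only at the last visit, it estimates 0.5/4 = 0.125 mm. Neither is the 0.5 mm bone-loss difference on which the trial is sized.

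**The case against.** A reader might infer that coding placement values as zero necessarily breaks sphericity, so that bone-loss intervals are always too narrow and alpha is lost. The documents do not support that.

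- The zero rule applies at every visit, and the share of zeros at placement is unknown.
- Even with all placement values zero, sphericity holds exactly with equal follow-up SDs and ρ = 0.5. Below that the pooled error is too wide and the contrast is conservative.
- Unequal visit spacing does not by itself violate sphericity.
- The plan does not state the univariate form, a pooled-error contrast or a confidence interval. The largest figures in the table belong to a contrast that the plan permits but does not specify.
- The list of abbreviations expands MBL as a change. If changes from V2 are what enter the ANOVA, placement is not a separate level and the mechanism does not arise as described.
- Between-group differences could be read from the main effect, which holds 5% in every setting, and inflation of the overall group-by-time F is modest.

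All of this stands, and it limits the claim. It does not remove it. The main effect keeps its error rate while answering a different question from the primary endpoint. Silence on the form leaves the uncorrected version open after the data are seen. Nominal alpha for the pooled-error contrast depends on a particular variance pattern: at the same ρ = 0.5, the mild widening in setting B already gives 7.4%.

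**Conclusion.** The concern holds in limited form. The plan fixes neither the primary contrast nor the handling of sphericity, so control of the 5% error rate for bone loss cannot be confirmed. If the classical uncorrected analysis were used, the placement-to-last contrast would reject about 2.5% to 15% of the time and the group-by-time F about 5% to 8%, with the direction set by variances and correlations that the documents do not give. All SDs and correlations above are assumptions, and the range is not a bound; steeper widening would push the upper end further. Testing the change with its own variance gave 4.8% to 5.2% in every setting.

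This is a cheap improvement, not a must-fix: an open specification with a better, nearly free alternative, not a demonstrated error.

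**What to change.** In Statistical Considerations, state that the primary analysis is the between-group difference in patient-level MBL change from V2 to V10, with its 95% CI from the variance of that change. A two-sample test on the change is enough. A mixed model on the changes at the follow-up visits, with unstructured covariance and Kenward-Roger degrees of freedom, serves the same purpose and also uses patients with incomplete follow-up. Report the Greenhouse-Geisser p-value for any repeated-measures F test that is kept.

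The same edit should say which visits enter the longitudinal analysis. Clinical Measurements places a bone-level reading at V6, whereas the Schedule of Events shows standardized radiographs at V4 and V7 but not at V6. V2 and V10 both have one, so the primary contrast is unaffected.

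The cost is one or two sentences and no patients. The interval may be wider, and the test has fewer error degrees of freedom: with 17 per arm, 34 − 2 = 32 instead of 3 × 32 = 96. The critical t value rises from 1.985 to 2.037, about 2.6%.
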